Appendix 5: Contraceptive Guidance and Pregnancy Testing.....	59
Appendix 6: NANO Scale.....	62

Proprietary Information of MD Anderson

1

BACKGROUND & RATIONALE

1.1

BACKGROUND

Refer to the Investigator's Brochure (IB)/approved labeling for detailed background information on Ipilimumab and Pembrolizumab.

1.1.1

Disease Background

Cutaneous malignant melanoma is the most aggressive form of skin cancer, accounting for the large majority of skin cancer-related deaths. The global incidence continues to rise, with current estimates of 132,000 new diagnoses/year and 37,000 deaths [1]. Melanoma accounts for ~5% of all new cases of cancer in the United States (US). The incidence of melanoma continues to rise by almost 3% per year in the US, with 2014 estimates of 76,100 new diagnoses and 9,710 deaths. According to NCI Surveillance Epidemiology and End Results (SEER) data from 1975-2007, the five-year survival rate is 15% for late-stage disease [2]. The lifetime risk of developing invasive melanoma has been dramatically increasing, and the overall mortality from melanoma continues to rise [3], [4], [5].

Brain metastasis develops in ~50% of subjects with metastatic melanoma; in 10 - 40% of these subjects, the brain is the first site of relapse. Progressive disease in the brain is the major cause of tumor-related death in subjects with melanoma who develop metastases in this site [6]. The median survival is 4 months after diagnosis [7]. The limited activity of available agents, along with relative resistance to radiotherapy and poor central nervous system (CNS) penetration of most chemotherapeutic agents, make this one of the most daunting problems in oncology [8].

There is no optimal systemic or local therapy for melanoma metastatic to the brain. Therapy for small, single lesions or a limited number of metastases consists of surgery or stereotactic radiotherapy (SRT), with a moderate local control rate but a high incidence of new lesions that are neither prevented by nor responsive to whole brain radiation. Temozolomide, a drug with very high CNS penetration, has been studied in this setting but has a response rate of <10% in both the CNS and overall, so it contributes little benefit and has no apparent synergy with radiotherapy [6], [9], [10], [11]. Combining any of these approaches with whole brain irradiation has been of little value in the management of these subjects [12]. While antibodies are not believed to cross an intact blood-brain barrier, activated T-cells may be able to penetrate the blood brain barrier, providing a rationale for testing immunomodulatory therapies in this setting [13], [14]. Previously reported results from the Phase 2 study (CA184042) of ipilimumab monotherapy showed similar clinical benefit in the brain and systemically, with durable disease control of 24% (CNS) and 27% (extra-cranial) of these patients, providing a rationale for further study of promising immunotherapies in melanoma patients with brain metastases [15].

Similarly, ipilimumab combined with fotemustine was associated with a disease control rate (complete response [CR] + partial response [PR] + stable disease [SD]) of 50% (10/20) in patients with asymptomatic brain metastases in a Phase 2 trial (NIBIT-M1) [16]. In a Phase 1 dose escalation study (CA209004), the combination of nivolumab and ipilimumab was studied in subjects with unresectable or metastatic melanoma. An objective response rate of 53% was observed when patients were treated with the combination regimen (ipilimumab 3 mg/kg + nivolumab 1 mg/kg every 3 weeks x 4); an additional benefit of prolonged stable disease or minor response occurred in another ~20% of patients [17]. Since brain metastases in melanoma are the most frequent cause of death from this disease and the brain is a frequent site of failure even in subjects who achieve control of extra-cranial disease with systemic therapy, it is essential to discover whether the combination of ipilimumab plus pembrolizumab can provide similar promise to patients whose melanoma has metastasized to the brain.

Proprietary Information of MD Anderson

1.1.2 Pharmaceutical and Therapeutic Background

1.1.2.1 Ipilimumab

Ipilimumab (Yervoy®) is an immunoregulatory agent that blocks CTLA-4 to promote antitumor immunity. In a Phase III study of 676 subjects with unresectable or metastatic melanoma whose disease had progressed while receiving prior therapy for metastatic disease, ipilimumab administered at 3 mg/kg q3w for up to 4 doses with or without a gp100 peptide vaccine was compared with gp100 alone [40]. The median overall survival (OS) was 10.1 months and 10.0 months for the ipilimumab alone and ipilimumab plus gp100 arms respectively, while the median OS was 6.4 months for the gp100 alone arm ($p<0.001$). An overall response rate (ORR) of 10.9% was observed in ipilimumab alone arm, while the ipilimumab plus gp100 arm and gp100 alone arm had lower response rates, 5.7% and 1.5%, respectively. The median duration of response was 11.5 months in the ipilimumab plus gp100 arm, and not reached in the ipilimumab alone arm with a median follow-up period of 27.8 months. The median time to progression was 2.86 months for the ipilimumab alone arm and 2.76 months for the other two arms. In the ipilimumab alone arm, 97% of the subjects experienced an adverse event (AE) and grade 3-4 AEs occurred in 46% of the subjects. The most common AEs related to ipilimumab were immune related events, which occurred in approximately 60% of the subjects treated with ipilimumab and 32% of the subjects treated with gp100. The frequency of grade 3-4 immune-related AEs was 15%. The immune-related AEs most often affected the skin and gastrointestinal tract, including pruritus, rash, vitiligo, diarrhea, and colitis.

Based on the above Phase III trial, ipilimumab was approved by the FDA for treatment of subjects with unresectable or metastatic melanoma and by the European Commission for treatment of subjects with previously-treated advanced melanoma. The recommended regimen is 3 mg/kg administered q3w for a total of four doses.

A reduction of the risk of death (28%; $p<0.001$) was also demonstrated for ipilimumab in the first - line setting when combined with dacarbazine in comparison with dacarbazine alone, and the ORRs were 15% and 10% (Investigator assessment per RECIST 1.1) in the ipilimumab/dacarbazine arm and dacarbazine alone arm, respectively [41]. The ipilimumab/dacarbazine arm did show a statistically significant progression-free survival (PFS) improvement [hazard ratio (HR) 0.76; $p=0.006$] over the dacarbazine alone arm. Median OS in the ipilimumab/dacarbazine and dacarbazine arms was 11.2 months and 9.1 months, respectively. The one-year OS rate for the ipilimumab/dacarbazine arm was 47.3%; the rate for the dacarbazine arm was 36.3%.

In RCC, a Phase I/II trial by Yang revealed an ORR 9.8% [42], across different dose levels, in subject's treatment naïve and previously treated with interleukin-2. Given the greater response rates seen with tyrosine kinase inhibitors, ipilimumab was not further developed as monotherapy in RCC. Refer to the approved labeling for detailed background information on Ipilimumab.

1.1.2.2 Pembrolizumab

The importance of intact immune surveillance in controlling outgrowth of neoplastic transformation has been known for decades [2]. Accumulating evidence shows a correlation between tumor-infiltrating lymphocytes (TILs) in cancer tissue and favorable prognosis in various malignancies [3], [4], [5], [6], [7]. In particular, the presence of CD8+ T-cells and the ratio of CD8+ effector T-cells / FoxP3+ regulatory T-cells seems to correlate with improved prognosis and long-term survival in solid malignancies such as ovarian, colorectal and pancreatic cancer, hepatocellular carcinoma, malignant MEL and RCC. TILs can be expanded ex vivo and re- infused, inducing durable objective tumor responses in cancers such as melanoma [8], [9].

The PD-1 receptor-ligand interaction is a major pathway hijacked by tumors to suppress immune control. The normal function of PD-1, expressed on the cell surface of activated T-cells under healthy conditions, is to down-modulate unwanted or excessive immune responses, including autoimmune reactions. PD-1 (encoded by the gene Pdcd1) is an Ig superfamily member related to

Proprietary Information of MD Anderson

CD28 and CTLA-4 which has been shown to negatively regulate antigen receptor signaling upon engagement of its ligands (PD-L1 and/or PD-L2) [10], [11]. The structure of murine PD-1 has been resolved [12]. PD-1 and family members are type I transmembrane glycoproteins containing an Ig Variable-type (V-type) domain responsible for ligand binding and a cytoplasmic tail which is responsible for the binding of signaling molecules. The cytoplasmic tail of PD-1 contains 2 tyrosine-based signaling motifs, an immunoreceptor tyrosine-based inhibition motif (ITIM) and an immunoreceptor tyrosine based switch motif (ITSM). Following T-cell stimulation, PD-1 recruits the tyrosine phosphatases SHP-1 and SHP-2 to the ITSM motif within its cytoplasmic tail, leading to the dephosphorylation of effector molecules such as CD3 ζ , PKC θ and ZAP70 which are involved in the CD3 T-cell signaling cascade [10], [13], [14], [15]. The mechanism by which PD-1 down modulates T-cell responses is similar to, but distinct from that of CTLA-4 as both molecules regulate an overlapping set of signaling proteins [16], [17]. PD-1 was shown to be expressed on activated lymphocytes including peripheral CD4+ and CD8+ T-cells, B-cells, regulatory T cells (Tregs) and Natural Killer cells [18], [19]. Expression has also been shown during thymic development on CD4-CD8- (double negative) T-cells as well as subsets of macrophages and dendritic cells [20]. The ligands for PD-1 (PD-L1 and PD-L2) are constitutively expressed or can be induced in a variety of cell types, including nonhematopoietic tissues as well as in various tumors [1], [16], [21], [22], [23]. Both ligands are type I transmembrane receptors containing both IgV- and IgC-like domains in the extracellular region and contain short cytoplasmic regions with no known signaling motifs.

Binding of either PD-1 ligand to PD-1 inhibits T-cell activation triggered through the T-cell receptor. PD-L1 is expressed at low levels on various non-hematopoietic tissues, most notably on vascular endothelium, whereas PD-L2 protein is only detectably expressed on antigen-presenting cells found in lymphoid tissue or chronic inflammatory environments. PD-L2 is thought to control immune T-cell activation in lymphoid organs, whereas PD-L1 serves to dampen unwarranted T-cell function in peripheral tissues [16]. Although healthy organs express little (if any) PD-L1, a variety of cancers were demonstrated to express abundant levels of this T-cell inhibitor. High expression of PD-L1 on tumor cells (and to a lesser extent of PD-L2) has been found to correlate with poor prognosis and survival in various cancer types, including RCC [24], pancreatic carcinoma [25], hepatocellular carcinoma [26], and ovarian carcinoma [27]. Furthermore, PD-1 has been suggested to regulate tumor-specific T-cell expansion in subjects with melanoma [28]. This suggests that the PD-1/PD-L1 pathway plays a critical role in tumor immune evasion and should be considered as an attractive target for therapeutic intervention.

Pembrolizumab (previously known as SCH 900475 and MK-3475) is a potent and highly selective humanized monoclonal antibody (mAb) of the IgG4/kappa isotype designed to directly block the interaction between PD-1 and its ligands, PD-L1 and PD-L2.

Based on the preliminary clinical data, PD-1 inhibitors such as pembrolizumab appear to be attractive candidates for pursuing the above goal. Nivolumab has an observed ORR of 28% in MEL subjects; pembrolizumab has shown a promising response rate of 25% in melanoma subjects who have received prior IPI treatment in KEYNOTE 002 [29]. Specifically, a response rate of 36% was observed with pembrolizumab in melanoma subjects who have not received prior IPI treatment in KEYNOTE 006 [30]. This response rate is much higher than the 11-15% response rate observed with IPI in IPI registration trials.

On September 4, 2014, the Food and Drug Administration (FDA) granted accelerated approval for pembrolizumab 2mg/kg q3w in advanced melanoma following disease progression with IPI and, if BRAF V600 mutation positive, a BRAF inhibitor [31]. The approval was based on a strong efficacy and safety profile demonstrated in 4 melanoma expansion parts of the Phase I trial (KEYNOTE 001) [32]; the B2 IPI-refractory population was the subject population for the approval. On December 18, 2015, the FDA granted full approval of pembrolizumab for the treatment of subjects with unresectable or metastatic MEL with pembrolizumab based on KEYNOTE 002 and 006 [33], [34].

Refer to the FDA approved labeling for additional detailed background information on Pembrolizumab.

Proprietary Information of MD Anderson

1.2

RATIONALE

The incidence of melanoma is rising, and despite efforts of early diagnosis, metastatic melanoma remains a challenge for the treating oncologist. Recently, monoclonal antibodies against different immune checkpoints have been revolutionizing the treatment of metastatic and unresectable melanoma, leading to prolonged OS in a subgroup of patients with advanced melanoma [1]. Despite the unprecedented durable response rates observed with cancer immunotherapies, the majority of patients do not benefit from the treatment (primary resistance), some responders relapse after a period of response (acquired resistance), and heterogeneous responses have been seen even between distinct tumors within the same patient [2]. Despite these advances, up to 50-60% of melanoma patients will also develop brain metastasis (MBM) during their course of treatment [3].

However, a recent study has reported a response rate of 22% for single agent pembrolizumab in MBM, with responses being durable. Importantly, two recent studies have shown that in patients with untreated MBM, the combination of ipilimumab and nivolumab yielded response rates of up to 55%. In CheckMate 204, 75 patients were treated with the ipilimumab (3mg/kg Q3 weeks x4) in combination with nivolumab (1mg/kg x4), followed by nivolumab 3mg/kg every 2 weeks until progression or unacceptable toxicity (and a maximum of 2 years). At over 9 months of follow-up, 21% of patients had reached a complete response in the brain, and the median PFS was not reached. In addition to 33% that had a partial response, 5% of patients benefitted by having stable disease. Median time to response was fast at 2.8 months (range 1-11 months). Duration of response had not been reached at time of report. Similarly as the combination trial reported by Larkin et al., 52% of patients experienced grade 3 and 4 toxicities, and 25% had to discontinue study drug. Importantly, treatment related nervous system adverse events were rare, and grade 3 and 4 toxicities only occurred in 8% of the patients [4], [5]. A second trial led by the Australian group (ABC trial) randomized patients with MBM to receive either combination therapy with ipilimumab and nivolumab, or to receive single agent nivolumab at 3mg/kg q2 weeks. Patients had a higher number of brain metastases, but in treatment naïve patients response rate for patients receiving the combination was 50% (15% CR, 35% PR), and stable disease was achieved in 10%. Of the 26 patients treated in this cohort, 46% experienced Grade 3 and 4 toxicities, leading to 27% discontinuation rate.

Recently, KEYNOTE-029 reported the outcomes of 153 melanoma patients, treated with the combination of pembrolizumab 2 mg/kg plus intravenous ipilimumab 1 mg/kg every 3 weeks for four doses, followed by intravenous pembrolizumab 2 mg/kg every 3 weeks for up to 2 years or disease progression, intolerable toxicity, withdrawal of consent, or investigator decision. Estimated 1 year PFS was 69% (95% CI 60-75), and estimated 1 year OS was 89% (95% CI 83-93). 61% of patients achieved an objective response. Grade 3 and 4 toxicities occurred in 45% of patients, which was less than the grade 3 and 4 toxicities reported for the combination of ipilimumab (3mg/kg) and nivolumab (1mg/kg in combination with ipilimumab, followed by 3mg/kg as single agent). While promising, patients with MBM were excluded.

We hypothesize that using low dose ipilimumab in combination with pembrolizumab will be beneficial to patients that had previously progressed on anti-PD1 therapy, and will have similar response as in reported trials using nivolumab and ipilimumab for PD-1 naïve patients with MBM, however, with less grade 3/4 events. In addition, we will evaluate the efficacy of this regimen in a small subset of patients that are treatment naïve to anti-PD1 agents.

Proprietary Information of MD Anderson

2 OBJECTIVES

2.1 PRIMARY OBJECTIVE

To assess clinical benefit rate (CBR), defined as CR + PR + SD > 6 months, in the brain in subjects with MBM per modified RECIST 1.1 criteria who are treatment naïve to anti-PD-1 agents in the metastatic setting (prior adjuvant anti-PD1 allowed. See inclusion and exclusion criteria).

2.2 SECONDARY OBJECTIVES

1. To assess CBR in the brain in subjects with MBM per modified RECIST 1.1 in patients who previously progressed on PD-1 inhibitors.
2. To assess OS and PFS.
3. To evaluate the brain-specific safety and tolerability of the combination regimen in subjects with or without SRT received prior to study entry, or on study.
4. To evaluate cytokine levels and changes in the T-cell population in the cerebrospinal fluid (CSF) and blood in patients treated with combination low dose ipilimumab and pembrolizumab.
5. To assess changes in relative apparent diffusion coefficient as measured by MRI as an early predictor of response.
6. To assess changes in circulating cfDNA as determinants of response and/or markers of early progression.
7. To evaluate molecular and immunological changes in extracranial lesions.

2.3 EXPLORATORY END POINT

Radiotherapy-assisted PFS defined as time from study treatment initiation to the first occurrence of disease progression or death from any cause, whichever occurs first, as determined by the investigator according to RECIST v1.1 modified by excluding ≤ 5 lesions that can be treated by SRT from the sum of largest diameters from baseline onwards.

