3 STUDY DESIGN

This is a two-cohort, open-label, single site phase II study. There will be no dose escalation or expansion cohort. A total of 30 subjects will be recruited for this study; 25 in Cohort A and 5 in Cohort B.

- Cohort A: Patients who are treatment naïve to anti- PD-1 agents in the metastatic setting (prior adjuvant anti-PD1 allowed. See inclusion and exclusion criteria).
- Cohort B: Patients who previously progressed on PD-1 inhibitors.

All subjects will be treated with the same dose for both ipilimumab and pembrolizumab. The induction period consists of: intravenous pembrolizumab 200 mg plus intravenous ipilimumab 1 mg/kg every 3 weeks for up to four doses, followed by a maintenance period: intravenous pembrolizumab 200 mg every 3 weeks (as tolerated) for up to 2 years or disease progression, intolerable toxicity, withdrawal of consent, death or investigator decision.

The use of SRT (single episode) for disease progression of ≤ 5 brain lesions is permitted in this study

Low-Dose Ipilimumab with Pembrolizumab – University of Texas MD Anderson Cancer Center

2018-0875, Version 1.6

Proprietary Information of MD Anderson

per protocol-defined guidelines. Any subject who receives SRT while on study will be observed for a protocol-defined period before treatment with the study drug(s) can be resumed. The length of the observation period is determined by when in the course of treatment the subject receives SRT - during induction (pembrolizumab plus ipilimumab) or during maintenance treatment (pembrolizumab q3 weeks). Any subject who meets criteria for discontinuation following SRT will proceed to follow-up. All subjects who are discontinued from treatment will continue to be followed for safety, progression, and OS after discontinuation of study medication.

Table 1: Study Drugs and Administration Details

Study Drug	Dose
Ipilimumab	1 mg/kg every 3 weeks for up to four doses
	No Additional Ipilimumab for Study Treatment
Pembrolizumab	200mg in combination with ipilimumab, every 3 weeks, up to four doses, followed by
	Administer 200mg as a single agent every 3 weeks up to 35 doses or until disease progression or unacceptable toxicity, withdrawal of consent, or investigator decision.

Proprietary Information of MD Anderson

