4.1.2 Exclusion Criteria

1. History of known leptomeningeal involvement (lumbar puncture not required).
2. Previous stereotactic or highly conformal radiotherapy within 1 weeks before the start of dosing for this study. **Note:** The stereotactic radiotherapy field must not have included the brain index lesion(s).
3. Subjects previously treated with SRT > 5 lesions in the brain.
4. Brain lesion size > 3 cm.
5. Prior checkpoint inhibitor therapy (which may include molecularly-targeted agents, IFN- α , and ipilimumab):
 - Patients who received ipilimumab as adjuvant or neoadjuvant therapy must have a 6-month washout before receiving any dosing on this study.
 - Cohort A: Prior anti-PD1 in the adjuvant setting is allowed, but patients must not have progressed within six months of the last dose of adjuvant therapy.
 - Cohort B: Patients with unresectable metastatic melanoma who received either anti-PD-1 or PDL-1 in the past are eligible. Washout period a minimum 3 weeks.
6. Subjects with an active, known or suspected autoimmune disease. Subjects with type I diabetes mellitus, hypothyroidism only requiring hormone replacement, skin disorders (such as vitiligo, psoriasis, or alopecia) not requiring systemic treatment, or conditions not expected to recur in the absence of an external trigger are permitted to enroll.
7. Subjects with major medical, neurologic or psychiatric condition who are judged as unable to fully comply with study therapy or assessments should not be enrolled.
8. Subject has a history of a second malignancy, unless potentially curative treatment has been completed with no evidence of malignancy for 2 years. Note: The time requirement does not apply to participants who underwent successful treatment of superficial bladder cancer, in situ cervical cancer, or other in-situ cancers. Subjects with a completely treated prior malignancy and no evidence of disease for ≥ 2 years are eligible.
 - a. Skin Cancer Exclusion: Please note that basal cell carcinoma and squamous cell carcinoma is exempt from needing resection prior to treatment. (Resection can be completed after the start of treatment).
9. Has a known history of or is positive for hepatitis B (hepatitis B surface antigen [HBsAg] reactive) or hepatitis C (hepatitis C virus [HCV] RNA [qualitative] is detected).

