4.2.4 Treatment beyond Progression

Study treatment may be continued beyond progression per RECIST v1.1 if pseudoprogression due to the effects of immunotherapy is suspected to have occurred or if disease progression is limited to \leq 5 intracranial lesions that can be controlled with stereotactic radiotherapy (SRT). Clinically stable patients who have a favorable benefit-risk ratio may continue study treatment beyond progression per RECIST v1.1 for either reason if all of the following criteria are met:

- Clinically stable patient with evidence of clinical benefit and favorable benefit-risk ratio as determined by the investigator
- Absence of symptoms and signs (including laboratory values, such as new or worsening hypercalcemia) indicating unequivocal disease progression
- No decline in Eastern Cooperative Oncology Group (ECOG) Performance Status that can be attributed to disease progression
- Absence of tumor progression at critical anatomical sites (e.g. leptomeningeal disease) that cannot be managed by protocol-allowed medical interventions
- Documented investigator/patient discussion of treatment options alternative to continuing study treatment at the time of RECIST v1.1-defined disease progression

Study treatment will be discontinued in any patient who continues treatment beyond disease progression per RECIST v1.1 if clinical deterioration because of disease progression occurs at any time or if persistent disease growth is confirmed on follow-up disease assessments performed approximately four weeks later. Post-progression assessments may be conducted sooner if necessary e.g. due to clinical progression. The disease status of patients who continued study treatment and underwent intracranial SRT will be determined by the investigator according to RECIST v1.1 modified by excluding any treated lesions from the sum of largest diameters from baseline onwards.

Proprietary Information of MD Anderson

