4.4.13 Tumor Imaging and Assessment of Disease

All subjects will undergo CT scanning and volumetric MRI of the brain at the time points specified in the Schedule of Events in Section 5. CT and MRI scans will be assessed locally per the modified RECIST 1.1 criteria. Up to 5 systemic and 5 brain lesions will be followed for efficacy per the criteria.

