Appendix 2: RECIST v1.1

Response Evaluation Criteria in Solid Tumors (RECIST v1.1 Criteria)

The RECIST criteria should be used to assess response to treatment. Only patients with measurable disease should be entered in the study. Measurable extracranial disease is defined as the presence of one lesion that can be accurately measured in at least one dimension (longest diameter to be recorded) as ≥ 2.0 cm with conventional techniques (or as ≥ 1.0 cm by spiral CT). Evaluable lesions should be followed for the assessment of response. Non-measurable lesions include bone lesions, ascites, pleural/pericardial effusion, lymphangitic carcinomatosis, abdominal masses that are not confirmed by CT, and cystic lesions. Disease progression and response evaluations for intracranial and extracranial disease will be determined according to the definitions established in the Response Evaluation Criteria in Solid Tumours (RECIST v1.1). Minor modifications will be applied to the assessment of intracranial lesions:

- General: target lesions should be representative of the subject's baseline tumor burden and should be selected based on their size (i.e. lesions with the longest diameter) and their suitability for accurate repeat assessment.
- Intracranial lesions: (the modifications to RECIST v1.1. impact the number and the minimal size of the target lesions selected at baseline) up to five lesions should be selected as target lesions; all brain lesions in excess of these five target lesions have to be regarded as non-target lesions. Measurable lesions are defined as those that can be accurately measured in at least one dimension with the longest diameter ≥ 5 mm when evaluated with contrast-enhanced MRI. Contrast-enhanced MRI is the only imaging modality accepted for assessment of intracranial lesions.
- Extracranial lesions: up to two lesions per organ representative of all involved organs should be selected as target lesions; the total number of target lesions should not exceed five and all lesions in excess of these five target lesions have to be regarded as non-target lesions.

Baseline Documentation of Intracranial Target and Non-Target Lesions

- All baseline lesion assessments must be performed within 28 days of the first dose of study treatment.

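### Sections 2.3 and 4.2.4 exclude different lesions, so radiotherapy-assisted PFS can drop target lesions that were never irradiated

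*Combined protocol and SAP*

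**What the plan says.** Section 2.3 is the only definition of radiotherapy-assisted PFS. It runs from the start of treatment to investigator-determined progression or death, using RECIST v1.1 after leaving out up to five "lesions that can be treated by SRT from the sum of largest diameters from baseline onwards". It does not require that SRT was given, does not say when treatability is judged, and does not restrict the lesions to the brain.

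Section 4.2.4 has a parallel rule. It opens: "The disease status of patients who continued study treatment and underwent intracranial SRT will be determined by the investigator". The criteria it then names are RECIST v1.1 "modified by excluding any treated lesions from the sum of largest diameters from baseline onwards". Here the patient must have had SRT, and only the treated lesions leave the sum.

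Related text:
- Section 3: "The use of SRT (single episode) for disease progression of ≤ 5 brain lesions is permitted in this study". Section 4.3.1.1 leaves the choice to give SRT to the investigator.
- Appendix 2, intracranial lesions: "up to five lesions should be selected as target lesions". Section 4.4.13 agrees: "Up to 5 systemic and 5 brain lesions will be followed for efficacy per the criteria".
- Section 6.2.2 defines ordinary PFS and plans a Kaplan-Meier analysis of it. Section 6.2 does not mention radiotherapy-assisted PFS.

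**The concern.** A progression endpoint should follow from measurements and from what was done to the patient. Under the literal wording of Section 2.3, it depends on an opinion about what could be done. The documents do not define which lesions are treatable by SRT, so the investigator who determines progression also decides which lesions enter the sum.

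SRT is optional and limited to one episode, so a lesion can be treatable and never irradiated. If such a lesion is left out from baseline and then grows, that growth does not register as target-lesion progression. Two analysts, one following Section 2.3 and the other Section 4.2.4, could assign different event dates to the same patient. Among events caused by target-lesion growth in the dropped lesions, the literal rule can only remove or delay them, so the endpoint would tend to look longer.

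**Working it through.** The documents attach no sample size, event count or rate to this endpoint, so there is no stated figure to reproduce. The check compares the two texts and then works through an example.

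**Side by side**

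| | Section 2.3 | Section 4.2.4 |
|---|---|---|
| Patients | all | those who continued treatment and had intracranial SRT |
| Lesions left out | up to five that could receive SRT | those that received SRT |
| From when | baseline | baseline |
| Effect if SRT is never given | up to five lesions may still leave the sum | none |

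**How far the literal rule reaches.** At most 5 brain target lesions are followed, and the Section 2.3 cap is also 5. Brain targets that may be left in the sum: 5 − 5 = 0.

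**Illustration (assumed sizes, not from the documents).** Five brain targets of 20, 15, 12, 10 and 8 mm sum to 65 mm. Two extracranial targets of 20 mm each stay stable (40 mm). Every brain target that stays in the sum grows by 50%. Appendix 2 sets target-lesion progression at a rise of at least 20% over the smallest sum, with an absolute rise of 5 mm. The baseline sum is taken as the smallest.

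1. No SRT given, nothing excluded (the result when the Section 4.2.4 rule does not apply): 65 + 40 = 105 mm becomes 97.5 + 40 = 137.5 mm. Change 32.5/105 = +31%. Progression.
2. No SRT given, Section 2.3 read literally, all five brain targets judged treatable and dropped: 40 mm stays 40 mm. Change 0%. No target-lesion progression.
3. SRT given to the 20 mm lesion only, Section 4.2.4 wording: 45 + 40 = 85 mm becomes 67.5 + 40 = 107.5 mm. Change 22.5/85 = +26%. Progression. On the brain sum alone, 45 to 67.5 mm is +50%, also progression.

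Cases 1 and 2 are the same patient with the same scans; only the exclusion rule differs.

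**What the exclusion does not touch.** It acts only on the sum of diameters. Appendix 1 also counts clear growth of non-target lesions, new lesions and marked clinical decline as progression, and Appendix 2 also allows progression on clinical grounds. Extracranial progression and death remain events. Appendix 1 adds immunotherapy guidance under which a new lesion in the first six months is not progression by itself; that is separate from the Section 2.3 exclusion.

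**The case against.** The best defence is that the intended meaning is plain. The endpoint is called radiotherapy-assisted. Section 4.2.4 first uses treatability to decide who may stay on treatment, then excludes treated lesions in words that end exactly as Section 2.3 does. Section 2.3 may be shorthand for that procedure. Dropping lesions in a patient who never has radiotherapy is an odd reading, since nothing then assists. This is probably right about intent, but it does not repair the rule. Section 4.2.4 moves from treatable to treated when it defines disease status, and Section 2.3 does not.

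A reader might infer several stronger points that the documents do not support:
- **That brain progression vanishes from the endpoint.** Only growth of excluded target lesions can be lost; the other routes to progression remain.
- **That Section 2.3 can empty the brain sum while Section 4.2.4 always keeps a brain target.** Section 4.3.1.1 asks for a remaining unirradiated target lesion as a condition for staying on study, but does not say it must be intracranial. A patient with extracranial targets might have all five brain targets irradiated and excluded under Section 4.2.4 too.
- **That every lesion is treatable because of the size limit.** The exclusion "Brain lesion size > 3 cm" applies at entry. It is not a limit at progression, and treatability is not defined by size.

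It is also fair to say that the investigator chooses who receives SRT, so tying the exclusion to treatment given leaves some discretion. It does tie the endpoint to a recorded act.

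**Conclusion.** The inconsistency is real and should be reconciled. Section 2.3 selects lesions by whether SRT is possible and Section 4.2.4 by whether it was given. Taken literally, the former allows never-irradiated target lesions to leave the sum from baseline, with later or missing target-lesion events as the result.

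The direction for those events is clear, but the size is not computable: the documents give no PFS rate, no SRT rate and no distribution of brain lesion numbers. The 31% against 0% contrast rests on invented lesion sizes and shows only that the two rules can disagree on the same scans.

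The consequence is small. The endpoint is exploratory, investigator-assessed and has no planned test. A reader might infer a threat to the main result, but CBR and the sample size do not use this definition. This is a minor, inexpensive correction.

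**What to change.** Align the endpoint text in Section 2.3 with Section 4.2.4. Suggested wording: progression is determined by modified RECIST v1.1, leaving out of the sum, from baseline onwards, only the intracranial lesions (up to five) that received protocol-permitted SRT on study; progression in a lesion that could have been irradiated but was not counts as an event.

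It would help to add one sentence on how new or non-target brain lesions given SRT are counted. They are never in the sum, so neither section covers them. Ordinary PFS is already planned in Section 6.2.2, so no further comparison analysis is needed.

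The cost is a few words and no new data. Radiotherapy-assisted PFS may come out slightly shorter. The change concerns the endpoint definition only and alters no rule on who receives SRT or continues treatment.
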